4.11 Safety Analyses

4.11.1 Adverse Events

Only treatment-emergent AEs will be included in the summaries for safety population.

Protocol:

Post-market clinical follow-up of a magnetic bone conduction implant

Protocol No:

CBAS5477

Version:

1.0

Page 15 of
18

A summary of subjects reporting at least one of the following AEs will be presented in an overview table:

- Any AE
- Any SAE
- Any Adverse Device Effect (ADE)
- Any Serious Adverse Device Effect (SADE)

Summaries per predefined AE, SOC and PT presenting n (%) of AEs and n (%) of subjects with at least one AE will be provided for:

- All AE
- All SAE
- All Adverse Device Effect (ADE)
- All Serious Adverse Device Effect (SADE)

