6.15 Test of Sound Processor on Softband

Between Visit 1 and Visit 2 (pre-operatively), the subjects will use the Baha Softband to test the sound processor during 1-2 weeks in different daily listening situations in order to get an impression of the hearing improvement he/she might anticipate post-surgery with the sound processor connected to the SP Magnet. The subject will use the selected sound processor as described in section 6.9. Instructions regarding use of the Baha Softband are described in the user manual for the product.

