8.6 Adverse Event analyses

Adverse Events will be analysed descriptively for the Safety population. Implant survival will be analysed and illustrated with a Kaplan-Meier survival curve.

Adverse Events and Serious Adverse Events will be coded with the MedDRA dictionary and tabulated by Preferred Term-code and System Organ Class-code and treatment.

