2 STUDY POPULATIONS

2.1 Definition of Study Populations

The final definition of the analysis sets (ITT, PP and Safety) will be taken at the clean file meeting before database lock.

Protocol:

Post-market clinical follow-up of a magnetic bone conduction implant

Protocol No:

CBAS5477

Version:

1.0

Page 8 of 18

2.1.1 *Intent-to-Treat Population (Full Analysis Set)*

The Intention-to-Treat population (ITT) will include all subjects who have received the surgical intervention.

2.1.2 *Per-Protocol Population*

The Per Protocol population (PP) will include subjects that have completed the investigation according to the protocol. Subjects that were incorrectly included or were considered major protocol violators should be removed from the PP population.

2.1.3 *Safety Population*

The Safety population consists of all surgically treated subjects

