3.3 Safety Variables

3.3.1 Adverse Events

Treatment emergent adverse events will be presented. Treatment emergent is defined as an event happening at or after surgery. Three predefined AE categories (Magnetic retention difficulties, Pressure related skin complications, Pain/Discomfort) will be used, and if other is checked those will be MedDRA (version 18.0) coded.

- Adverse Event (AE) is all reported events
- Adverse Device Effect (ADE) is events that is Related to the device (Probably) or Related to the procedure (Probably)
- Serious Adverse Event (SAE) is events that has been marked as Serious
- Serious Adverse Device Effect (SADE) is events that has been marked as Serious and also marked as Related to the device (Probably) or Related to the procedure (Probably)

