4.2 Patient Disposition and Data Sets Analyzed

The number of subjects included in each of the ITT, PP and Safety populations will be summarized. Subjects who completed the study and subjects who withdrew from study prematurely will also be presented with a breakdown of the reasons for withdrawal by treatment group for the ITT, PP and safety populations.

Reasons:

- Eligibility failed
- Intra-operative failure

Protocol:

Post-market clinical follow-up of a magnetic bone conduction implant

Protocol No:

CBAS5477

Version:

1.0

Page 13 of
18

- Subject non-compliance
- Major Protocol Deviation affecting the primary endpoint
- Lost to Follow-up
- Discretion of the investigator
- Subject withdrew Consent
- Intolerable Adverse Event
- Death
- Other

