6 CHANGES OF ANALYSIS FROM PROTOCOL

No changes of the analyses according to the protocol are made.

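### Adverse events, device deficiencies and withdrawals between consent and surgery have no scheduled collection before Visit 2 and no assured place in the planned tables

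*SAP*

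**What the plan says.** **Events.** SAP 4.11.1: "Only treatment-emergent AEs will be included in the summaries for safety population". SAP 3.3.1: "Treatment emergent is defined as an event happening at or after surgery". Protocol 8.6: "Adverse Events will be analysed descriptively for the Safety population". In both flowcharts (Protocol 5.3, SAP 1.2.1) the Adverse Events and Device deficiency rows start at Visit 2, the day of surgery, and SAP 3.3.3 starts deficiencies at day 0. Concomitant medication starts at Visit 1.

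**Populations.** SAP 2.1: "The Intention-to-Treat population (ITT) will include all subjects who have received the surgical intervention" and "The Safety population consists of all surgically treated subjects". PP is restricted to completers who followed the protocol. Surgery is not named there, but completion requires it.

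**Disposition.** SAP 4.2 promises a "breakdown of the reasons for withdrawal by treatment group for the ITT, PP and safety populations". Its list of reasons includes failed eligibility, intra-operative failure and withdrawn consent.

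**The period before surgery.** Consent and an enrolment number come before any procedure (Protocol 4.2). Soft tissue may be measured with a needle at Visit 1 (Protocol 6.5). The subject then uses the selected sound processor at home on a Softband for 1-2 weeks "in order to get an impression of the hearing improvement he/she might anticipate post-surgery" (Protocol 6.15).

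**The concern.** The protocol treats the time between consent and surgery as part of the investigation. Its adverse-event definition (6.27.1) covers any device used in the investigation and the procedures involved. Subjects are to be monitored for events throughout (6.27.2). A subject who chooses to discontinue is always to be asked about reasons and adverse events (4.4), with no condition that surgery has taken place. The sound processor worn at home is itself listed as part of the tested system (3.1).

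The collection schedule and the SAP do not follow this through. Events and deficiencies in that period may go unrecorded, and those that are recorded enter no planned summary. The report may also fail to show how many people tried the Softband and did not go on to surgery, or why. A reader needs that number to know to whom the hearing results apply, and to see how much of the drop-out allowance was spent before the first operation.

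**Working it through.** **1. The rules side by side.**

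| Item | Protocol text that reaches the pre-surgery period | Schedule or analysis rule |
|---|---|---|
| Adverse events | 6.27.1, 6.27.2, 4.4 | Flowcharts: from Visit 2. SAP 3.3.1 and 4.11.1: summaries from surgery |
| Device deficiencies | 6.26, defined for a medical device without a start date | Flowcharts and SAP 3.3.3: from day 0 |
| Withdrawals | 4.4, reasons asked | SAP 4.2: breakdown for ITT, PP and Safety |
| Medication and treatments | Flowchart: from Visit 1 | SAP 3.1.5, 3.1.6, 4.8, 4.9: reported from Visit 1, for ITT only |

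By these definitions, the number of pre-surgery adverse events entering an adverse-event summary is 0. So is the number of non-operated subjects entering any analysis population. Medicines and treatments before surgery are reported for operated subjects, while the events that might explain them are not.

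**2. Exposure.** Inputs: 52 subjects (Protocol 4.1.3) and 1-2 weeks of home use (Protocol 6.15). 52 x 1 week = 52 weeks, about 1 person-year. 52 x 2 weeks = 104 weeks, about 2 person-years. This assumes that all 52 complete the home trial.

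**3. The plan's own sample size.** The Softband comparison governs: 1.5 dB, SD 3 dB, 90% power, two-sided 0.05 (Protocol 8.2.2, SAP 1.4.2).
- Normal approximation: n = (SD x (1.960 + 1.282) / difference)^2 = (3 x 3.242 / 1.5)^2 = 42.0, rounded up to 43.
- Exact paired t: 44. With the stated 46, power is 0.913; a simulated paired permutation test gives 0.908.
- Drop-out: 46 / 0.9 = 51.1, rounded up to 52.

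The stated 46 and 52 are reproduced. The allowance is 52 - 46 = 6 subjects.

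**4. Stops before surgery.** The protocol includes 52 subjects and does not replace those who discontinue (4.1.3, 4.5). Reading 52 as a count of enrolled subjects, k stops before surgery leave at most 52 - k in ITT and Safety. The values of k below are illustrations.

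| k | 52 - k | k / 52 | Power, Softband comparison, no later loss | Subjects left and power after a further 10% loss |
|---|---|---|---|---|
| 1 | 51 | 1.9% | 0.938 | 45; 0.907 |
| 3 | 49 | 5.8% | 0.929 | 44; 0.900 |
| 6 | 46 | 11.5% | 0.913 | 41; 0.878 |

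Power uses the paired t with the plan's 1.5 dB and 3 dB. Power for the primary comparison (10 dB, SD 13 dB) stays above 0.99 in every row. At k = 6 with no later loss, the whole allowance has been used, and a breakdown confined to the three sets would show no withdrawals.

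**The case against.** Much of the opposing case stands, and it limits the point.

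- **Safety contrast.** A reader might infer that the plan makes the Softband look free of events. It does not. Attract versus Softband is compared on hearing variables only, the safety aim concerns the Attract System, the Softband is listed among other devices (Protocol 3.2), and no adverse-event table sets the two side by side.
- **Departure from protocol.** A reader might infer that SAP section 6, "No changes of the analyses according to the protocol are made", is contradicted. It is not. The protocol's own flowchart starts adverse events at Visit 2, and its Safety population is the operated subjects. The tension lies inside the protocol, and the SAP inherits it.
- **Bias.** A reader might infer that the Softband comparison is biased by who proceeds to surgery. Softband hearing is measured at Visit 1, before home use (Protocol 6.12 to 6.14), and the comparison is within subject. Bias would need selection on the error in those Visit 1 measurements, for which the documents give no evidence.
- **Enrolment above 52.** A reader might infer that more than 52 people are enrolled to yield 52 operated. That conflicts with 52 included and no replacement.
- **Other routes.** Serious events are reported within 24 hours with no surgery condition (Protocol 6.27.3). The Visit 2 enquiry might look back to Visit 1, although neither document says so. Table 14.1.1 carries no population label, SAP 4.2 also promises to present subjects who withdrew early, and listings are decided outside the SAP (7.3). Pre-surgery events and stops could therefore surface somewhere, but nothing in the plan ensures it. A look-back at Visit 2 would also miss anyone who never reaches Visit 2.
- **Surgery-based sets.** These are defensible. One exclusion criterion can be judged only during surgery, and the primary comparison cannot be measured in someone never implanted. This supports keeping the sets, but it does not justify leaving the other enrolled subjects uncounted.

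**Conclusion.** The point holds as a gap in collection and reporting. Events and deficiencies from consent to surgery, about 1-2 person-years of home use plus any Visit 1 needle measurement, have no scheduled collection before Visit 2 and no planned summary. Protocol 4.4, 6.27.1 and 6.27.2 nevertheless cover that time. Consented subjects who are not operated have no assured place in the disposition table, though they may use up part of the 52.

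The size of the second part depends on k, which is unknown, and on 52 counting enrolled subjects. The documents do not support a claim that any primary or secondary estimate is wrong. The matter should be corrected because the remedy is cheap and changes what is recorded and shown.

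**What to change.** 1. Reconcile Protocol 4.4, 6.27.1 and 6.27.2 with the two flowcharts and SAP 3.3.1 and 3.3.3: collect adverse events and device deficiencies from consent (Visit 1). List those before surgery separately, over all enrolled subjects. Leave the treatment-emergent summaries as they are.
2. In SAP 4.2 and Table 14.1.1, add an Enrolled set (all who consented), with the number not operated and the reasons. State in the report that the results apply to subjects who proceeded to surgery after a Softband trial.
3. Optional: tabulate Visit 1 unaided and Softband PTA4 for operated and non-operated subjects. These data are already collected, but the second group may be very small.

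Cost: one extra question before surgery, a short listing and one disposition row. The populations, tests and sample size stay as planned.

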6.23 Soft tissue status

At Visit 3-9, the investigator will examine the soft tissue at the implant site. In case of signs of e.g. inflammation, infection, skin necrosis or scar hypertrophy, the event shall be reported on the Adverse Event page in the CRF. If any treatment is provided, it shall also be recorded on the Concomitant medication page in the CRF.

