6.27.2 Handling and reporting of AEs

Subjects will be carefully monitored during the investigation for possible AEs and appropriate treatment of the subject will be initiated.

Any AE observed will be fully investigated by the investigator and documented in the case report form (CRF) including assessment of severity (mild, moderate or severe) and relationship to the medical device.

6.27.3 Reporting of SAEs and device deficiency that could have lead to a SAE

An investigator should report within 24 hours, after being aware of the event, an SAE or a device deficiency that could have lead to a SAE. The report should be sent as an e-mail attachment to Cochlear Bone Anchored Solutions AB. Instructions and contact information is available on the SAE form.

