3.3.3 Device deficiency and Soft tissue status

Device deficiency will be collected at d 0, d 10, w 4, w 6, w 12, m 6, m 12 and m 24.

- Has any device deficiency occurred?
 - Yes
 - No

Soft tissue status will be collected at d 10, w 4, w 6, w 12, m 6, m 12 and m 24.

- Any signs of infection, inflammation, skin necrosis and/or scar hypertrophy?
 - Yes
 - No

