Table 14.2.18	The Speech, Spatial and Qualities of Hearing Scale (SSQ) (Conductive/Mixed patients ITT Population)
Table 14.2.7.1	Surgery (ITT population)
Table 14.2.7.2	Surgery (PP population)
Table 14.2.8.1	Sound processor magnet, total and by magnet strength (ITT population)
Table 14.2.8.2	Sound processor magnet, total and by magnet strength (PP population)
Table 14.2.9.1	Usage (ITT population)
Table 14.2.9.2	Usage (PP population)
Table 14.3.1.1	Summary of Adverse Events (Safety Population)
Table 14.3.1.2	Adverse Events (AE), by Predefined AEs, System Organ Class and Preferred Term (Safety Population)
Table 14.3.1.3	Adverse Device Events (ADE), by Predefined AEs, System Organ Class and Preferred Term (Safety Population)
Table 14.3.1.4	Serious Adverse Events (SAE), by Predefined SAEs, System Organ Class and Preferred Term (Safety Population)
Table 14.3.1.5	Serious Adverse Device Events (SADE), by Predefined SADEs, System Organ Class and Preferred Term (Safety Population)
Table 14.3.2	Pain and Numbness (Safety Population)
Table 14.3.3	Device deficiency (Safety Population)
Table 14.3.4	Soft tissue status (Safety Population)
Table 14.3.5	Implant loss/removal and magnet loss/removal (Safety Population)

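### Investigators grade the severity of every adverse event, but no SAP summary uses it, so non-serious pressure-related skin events are reported with neither type nor grade

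*SAP*

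**What the plan says.** **Collection.** Protocol 6.27.2 has each adverse event documented in the CRF, "including assessment of severity (mild, moderate or severe) and relationship to the medical device". Protocol 6.23 sends skin findings to that form too: "In case of signs of e.g. inflammation, infection, skin necrosis or scar hypertrophy, the event shall be reported on the Adverse Event page in the" (the form just named). Soft tissue findings therefore reach the page on which severity is graded.

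**Classification.** SAP 3.3.1 defines four classes: AE, ADE, SAE and SADE. An ADE is an event judged probably related to device or procedure. For seriousness the rule is: "Serious Adverse Event (SAE) is events that has been marked as Serious". A SADE is both. Severity is not mentioned.

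**Coding.** SAP 3.3.1 sets up three predefined categories. The first is magnetic retention difficulties; the text continues: "Pressure related skin complications, Pain/Discomfort) will be used, and if other is checked those will be MedDRA (version 18.0) coded".

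**Summaries.** SAP 4.11.1 gives an overview of subjects with any event in each of the four classes, and then: "Summaries per predefined AE, SOC and PT presenting n (%) of AEs and n (%) of subjects with at least one AE will be provided for" the same four classes. Tables 14.3.1.1 to 14.3.1.5 in SAP 7.1 follow that layout.

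**Soft tissue.** SAP 3.3.3 reduces soft tissue status to one Yes/No item, "Any signs of infection, inflammation, skin necrosis and/or scar hypertrophy". SAP 4.11.2 presents it by visit, in Table 14.3.4.

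**The concern.** Protocol 7.2 names three risks of the transcutaneous coupling that cannot be fully removed: retention difficulties, pressure-related skin complications, and pain/discomfort. Protocol 1.2 makes mid- to long-term safety one of the two reasons for the study. A reader of the final report will want to know how many subjects had skin events and how bad those events were.

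The planned output answers only the first part. Seriousness does not replace severity. It is set by outcome criteria in protocol 6.27.1, such as hospitalisation, lasting disability or an important medical event, and an event can be graded severe without meeting any of them. At stake is a description of skin risk that the trial's own data could support and that the planned tables leave out.

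**Working it through.** The plan states no figure on this point, so the check sets the texts side by side.

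**1. Does severity appear in any planned AE output?**

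| SAP output | Seriousness | Relatedness | Category, SOC or PT | Severity |
|---|---|---|---|---|
| Table 14.3.1.1, overview | yes | yes | no | no |
| Table 14.3.1.2, all AEs | no | no | yes | no |
| Table 14.3.1.3, ADEs | no | yes | yes | no |
| Table 14.3.1.4, SAEs | yes | no | yes | no |
| Table 14.3.1.5, SADEs | yes | yes | yes | no |

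Severity is in 0 of 5 tables. Nor is AE severity in the variable definitions (3.3.1), the analysis text (4.11.1) or the figure list (7.2). SAP 7.3 leaves listings to be decided elsewhere.

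**2. Follow one event through the plan.** Take a non-serious skin event at the implant site.
- Filed under other: it gets a MedDRA term and its own PT row. Its type is visible; its grade is not.
- Filed under pressure-related skin complications: on the wording of SAP 3.3.1 it gets no MedDRA term. It is counted in that category's row in Table 14.3.1.2 and, if judged related, in Table 14.3.1.3. Neither type nor grade is visible.
- Had it been marked serious, it would also be counted in Table 14.3.1.4, again without a grade.

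**3. Does the soft tissue table fill the gap?** It pools 4 kinds of sign (infection, inflammation, skin necrosis, scar hypertrophy) into 1 binary item. The item is recorded at 7 visits (day 10, weeks 4, 6 and 12, months 6, 12 and 24). Inflammation and necrosis give the same Yes.

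**4. How do the other symptom measures compare?** Pain/discomfort keeps 4 levels at 5 visits (weeks 6 and 12, months 6, 12 and 24). Numbness keeps 3 levels at 7 visits. Both are shown by visit (SAP 3.3.2 and 4.11.2, Table 14.3.2). Soft tissue status is the clinical finding at the site that has no grading.

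**5. How much is left undetermined?** Let k be the number of subjects in the pressure-related skin row of Table 14.3.1.2. The number with at least one severe event can be any whole number from 0 to k, and the row reads the same. The documents give no expected k, so the gap cannot be sized further.

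**The case against.** The strongest reply is that much of the safety picture is already differentiated, and that nothing in the protocol's analysis section is breached.

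- *Other graded output exists.* Protocol 6.22 grades pain/discomfort from 0 to 3 by its effect on daily use of the processor, and the SAP reports all four levels. The SAP also plans daily hours of use, withdrawals for intolerable adverse events, and Kaplan-Meier figures for loss of implant and magnet. This stands. A reader might infer that no conclusion on risk can be drawn, or that pain suffers from the same gap. The documents support neither.
- *The AE tables separate some skin events.* This also stands. A reader might infer that mild inflammation and skin necrosis always count the same. That is strictly true only of Table 14.3.4 and of non-serious events filed in the same predefined category. An event filed as other is separated by preferred term, and a serious one appears in the SAE tables. Which of these applies depends on the box the site ticks, and none of them shows severity.
- *The protocol asks for no severity table.* Correct: protocol 8.6 plans tabulation by preferred term and system organ class. Leaving out severity is therefore an omission of collected data and no departure from a planned analysis. Coding is a different matter: 8.6 states MedDRA coding of adverse events without exempting any category.
- *Listings could show severity.* They could, and in a single-arm study of 52 planned subjects they could be read case by case. But SAP 7.3 commits to no content, and a listing gives no rates.
- *Seriousness may capture the important cases.* The definition in protocol 6.27.1 is broad, and the documents do not say what share of skin events would be serious. The point does not need that share; it concerns whatever remains non-serious.

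**Conclusion.** The point holds within limits. Severity is recorded for every AE and summarised for none. For non-serious events filed as pressure-related skin complications, the planned summary carries neither type nor grade, and the pooled soft tissue item does not supply them. The gap is the severity of skin and other non-pain AEs. Pain/discomfort is already graded by visit, and the efficacy analyses are not touched.

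The size is an absence: 0 of 5 AE tables use severity, and between 0 and k of the k subjects in the skin row could have had a severe event without any change in that row.

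This rests on two assumptions: that SAP 3.3.1 means what it appears to say, so that events in the predefined categories are not MedDRA coded; and that grades are completed as protocol 6.27.2 requires.

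It deserves a change to the SAP because it bears on a named residual risk and a stated rationale, and the grades are already in the CRF.

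**What to change.** 1. In SAP 3.3.1, define severity (mild, moderate, severe) as an AE variable, with worst severity per subject as the summary rule. Refer to it in 4.11.1.
2. Show Tables 14.3.1.2 and 14.3.1.3 by worst severity per subject within each predefined category and each PT.
3. Add any severe AE and any severe ADE to the overview, Table 14.3.1.1.
4. MedDRA-code the events in the three predefined categories as well, and summarise soft tissue findings by type from the AE page.

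Step 4 is preferable to splitting Table 14.3.4 by kind of sign. A reader might infer that each Yes can be traced to its AE entry. Protocol 6.23 requires an AE report but states no link to the visit-level item, and without coding an event in a predefined category carries no sign type. Table 14.3.4 can stay as it is.

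Cost: SAP wording, extra columns in existing tables, a little extra coding, and some small cells in tables that are descriptive anyway. Steps 1 to 3 need no new data. Step 4 assumes that the AE page holds a description of each predefined-category event that can be coded; data management should confirm this before the SAP is changed.

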1.2 Rationale

The rationale behind this post-market clinical investigation is to collect data regarding the usability and clinical performance of the Baha Attract System in subjects with hearing impairment that are candidates for Baha surgery:

- to evaluate the efficacy of the Baha Attract System in terms of hearing performance compared to the unaided situation and compared to a pre-operative test situation using the sound processor on a Baha Softband;
- to evaluate the mid- to long term safety of the Baha Attract System.

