1.2.1 Flowchart

Procedures and timing	Visit 1 Softband test	Visit 2 Surgery	Visit 3 Suture removal	Visit 4 Fitting	Visit 5	Visit 6	Visit 7	Visit 8 *	Visit 9 *
Day/Week/Month ¹	Pre-op	D 0	D 10	W 4	W 6	W 12	M 6	M 12	M 24
Time window			± 5d	± 1w	± 1w	± 2w	± 4w	± 4w	± 4w
Demographics	X								
Medical history	X								
Nicotine use	X								
Audiogram ²	X								X
Eligibility criteria	X								
Informed consent	X								
Soft tissue thickness	X or X								
Health Utility Index (HUI) ³	X ⁴						X		X
Abbreviated Profile of Hearing Aid Benefit (APHAB) ³	X ^{4,5}						X ⁶		X ⁶
The Speech, Spatial and Qualities of Hearing Scale (SSQ) ³	X ^{4,5}						X ⁶		X ⁶
BC Direct using BFS	X ⁷			X ⁸					X ⁹
Selection of sound processor	X								
Change of sound processor				X ⁹	X ⁹	X ⁹	X ⁹	X ⁹	X ⁹
Fitting of sound processor	X ⁷			X ⁸					X ⁹
Fine tuning of sound processor					X ⁹	X ⁹	X ⁹	X ⁹	X ⁹
Free field thresholds	X ^{5,7}			X ⁸			X ⁸	X ⁸	X ⁸
Speech recognition in noise	X ^{5,7}			X ⁸			X ⁸	X ⁸	X ⁸
Speech recognition in quiet	X ^{5,7}			X ⁸			X ⁸	X ⁸	X ⁸
Home test of sound processor on Softband	X →								
Surgery		X							
Surgery time		X							
Soft tissue thinning		X							
Bone polishing/removal		X							
Implant stability quotient		X							
Suture removal (if applicable)			X						
SP Magnet selection				X					
Magnetic retention force				X	X	X	X	X	X
Change of SP Magnet					X ⁹	X ⁹	X ⁹	X ⁹	X ⁹
Questions regarding: • Daily use of sound processor • Magnet retention • Change of soft pad					X	X	X	X	X
Pain/discomfort					X	X	X	X	X
Numbness			X	X	X	X	X	X	X
Soft tissue status			X	X	X	X	X	X	X
Loss/removal of Implant or Implant Magnet			X	X	X	X	X	X	X

STATISTISKA KONSULTGRUPPEN		Statistical Analysis Plan	
Protocol: Post-market clinical follow-up of a magnetic bone conduction implant		Protocol No: CBAS5477	
		Version: 1.0	Page 7 of 18

Device deficiency		X	X	X	X	X	X	X	X
Adverse Events		X	X	X	X	X	X	X	X
Concomitant medication/treatment	X	X	X	X	X	X	X	X	X
Extra visit									
Extra visit									

¹ The time between visits was calculated from Visit 2 (time 0); ² Only if the last audiogram that was performed on the subject was older than 6 months; ³ To be completed by the subject; ⁴ Before Softband test; ⁵ Unaided; ⁶ Aided; ⁷ With sound processor on Softband; ⁸ With Baha Attract System; ⁹ If needed; * Visit 8 and 9 are not included in the sixth months analysis

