4.11.2 Pain/discomfort, Numbness, Device deficiency and Soft tissue status

Pain/discomfort, Numbness, Device deficiency and Soft tissue status will be presented by visit.

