5 INTERIM ANALYSES

No interim analysis is planned. The main analysis is made at 6 month and another follow-up analysis at 24 months (18 months after the 6 months analysis).

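### The adverse event tables run cumulatively from surgery with no onset-period split or number at risk, so they cannot show how many subjects have a mid- to long-term event

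*SAP*

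**What the plan says.** Protocol section 1.2 gives as one of its two reasons for the study "to evaluate the mid- to long term safety of the Baha Attract System". Section 5 divides the 24 months into a 6-month investigation and a further 18 months of follow-up. The flowchart schedules adverse event collection at every visit from surgery (Visit 2) to month 24 (Visit 9).

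SAP 3.3.1 sets the counting window: "Treatment emergent is defined as an event happening at or after surgery". SAP 4.11.1 adds that "Only treatment-emergent AEs will be included in the summaries for safety population", and asks for "Summaries per predefined AE, SOC and PT presenting n (%) of AEs and n (%) of subjects with at least one AE", for AEs, SAEs, ADEs and SADEs in turn. Tables 14.3.1.1 to 14.3.1.5 follow that pattern. No onset period, number at risk, exposure-adjusted rate or time to first event is specified. Protocol 8.6 adds only MedDRA tabulation and a Kaplan-Meier curve for implant survival.

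Events are divided by type: "Three predefined AE categories (Magnetic retention difficulties, Pressure related skin complications, Pain/Discomfort) will be used", with other events coded in MedDRA. Some other safety outputs do carry time. SAP 4.11.2 says "Pain/discomfort, Numbness, Device deficiency and Soft tissue status will be presented by visit", and SAP 4.11.3 provides Kaplan-Meier figures for loss or removal of the implant and implant magnet. SAP section 5 plans a main analysis at 6 months and another at 24 months. The only stated limit on the 6-month data is a flowchart footnote: "Visit 8 and 9 are not included in the sixth months analysis".

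**The concern.** In these tables an infection a few days after surgery and a pressure sore at month 20 carry the same weight. The study was extended to 24 months in order to look beyond the healing phase, yet the tables that carry seriousness and relatedness do not distinguish that phase from what follows. Relatedness cannot stand in for timing, because SAP 3.3.1 defines an ADE as related to the device or to the procedure, so surgical events also enter the ADE and SADE tables.

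Two further consequences follow. Subjects who leave early remain in the denominator for late events. And no adverse event cut-off by subject is written for the 6-month analysis, so subjects enrolled early could contribute events from beyond their own month 6.

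At stake is whether a reader of the report can tell a device with healing-phase problems that then settle from one with problems that begin or persist later.

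**Working it through.** The documents give no adverse event rates and no accrual duration. The event counts and risks below are assumptions used to show what the tables can and cannot reveal.

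**Plan's own figure.** SAP 1.4.3: 46 evaluable subjects with 10% drop-out, 46 / 0.9 = 51.1, rounded up to 52. This reproduces. It enters here only as a denominator.

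**1. One cumulative table.** With early risk a and late risk b, taken as independent, the cumulative risk is 1 − (1 − a)(1 − b).
- a = 30%, b = 10%: 1 − 0.7 × 0.9 = 37.0%.
- a = 10%, b = 30%: 1 − 0.9 × 0.7 = 37.0%.

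Opposite safety profiles give the same 24-month figure.

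**2. Both planned tables together.** If early means up to month 6, the 6-month table would show 30% against 10% and so tell these two profiles apart. It still does not give the number of subjects with a late event. Suppose 20 of 52 are affected by month 6 and 28 of 52 by month 24.
- Minimum with an event in months 6 to 24: 28 − 20 = 8, the first-time subjects only (8/52 = 15.4%).
- Maximum: those 8 plus all 20 already affected = 28 (28/52 = 53.8%).

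Subtraction recovers only subjects whose first event is late. It recovers late event counts only if both tables use clean cut-offs.

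**3. Fitting as the boundary.** Fitting is scheduled at week 4, and neither analysis separates events there. Of the same 20 subjects affected by month 6, anywhere from 0 to 20 could have had an event between fitting and month 6.

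**4. Denominator.** If 10% are lost, 52 × 0.9 = 46.8 remain. Six late cases are then 6/52 = 11.5% or 6/46.8 = 12.8%, a difference of 1.3 percentage points. The 10% is a sample-size allowance, not a forecast of loss by month 24.

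**5. Cut-off at 6 months.** Assume a constant hazard h = −ln(1 − p)/6 per month for a true 6-month risk p, uniform accrual over A months, and data cut when the last subject reaches month 6. Follow-up is then uniform from 6 to 6 + A months, and the reported figure is the average of 1 − exp(−h × follow-up). The capped column stops counting at month 11, about the earliest Visit 8 (month 12 minus 4 weeks).

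| True risk | Accrual (months) | No cut-off | Capped at month 11 |
|---|---|---|---|
| 20% | 6 | 28.3% | 28.1% |
| 20% | 12 | 35.5% | 30.8% |
| 20% | 18 | 41.7% | 31.7% |
| 10% | 12 | 18.8% | 16.0% |
| 30% | 12 | 50.0% | 44.4% |

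The 20%, 12-month entry can be checked by hand: h = 0.0372, and 1 − (0.800 − 0.512)/(12 × 0.0372) = 35.5%.

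**The case against.** The strongest reply is that much of the safety output is already resolved by time. Soft tissue status is shown by visit from day 10 to month 24 and pain from week 6, numbness and device deficiency are also by visit, and losses have Kaplan-Meier curves, which handle unequal follow-up. A reader might infer that mid- to long-term safety cannot be assessed from this plan at all. The documents do not support that; the gap lies in the AE, ADE, SAE and SADE tables. Nor is there only a single cumulative count: there are two analyses, and the predefined categories isolate retention and pressure events, which presuppose a fitted magnet.

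These outputs narrow the gap without closing it. The soft tissue item in SAP 3.3.3 is one pooled yes/no question without seriousness or relatedness. With Visits 7, 8 and 9 at months 6, 12 and 24, a complication that starts and resolves between visits may appear only as an adverse event. The Kaplan-Meier curves cover losses alone. The predefined categories split by type, not time. Listings are left outside the SAP (7.3), so they cannot be relied on.

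A reader might also infer that the 6-month percentages will be distorted. That is only a possibility. If the footnote on Visits 8 and 9 is applied to adverse events, only those recorded between Visits 7 and 8, for instance at extra visits, could enter, and the effect depends on an accrual period that is not stated.

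Two practical objections stand. Onset periods crossed with SOC and PT in about 52 subjects give sparse cells. And the CRF is not available: SAP section 3.3 lists a date only for losses, and the treatment-emergent rule by itself needs only before or after surgery.

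**Conclusion.** The point holds for the adverse event tables and no further. As specified, they cannot state how many subjects have an event in the mid- to long-term period, although this is a declared aim. Under the assumed counts above, the two planned tables leave that number anywhere between 8 and 28 of 52.

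The denominator effect is minor, about 1.3 points in the example. The 6-month cut-off is a secondary matter: with an assumed true risk of 20% and accrual over 6 to 18 months, the reported figure could be 28% to 42% without a cut-off, or 28% to 32% if counting stops before Visit 8. It would be correct at 20% if events are in practice cut at each subject's Visit 7.

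All adverse event analyses are descriptive and single-arm, so no test, power or alpha is affected. The missing onset split is what makes this worth changing.

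**What to change.** In SAP 4.11.1, add an onset-period split to the overview table (14.3.1.1) and to the AE, ADE, SAE and SADE summaries (14.3.1.2 to 14.3.1.5): surgery to fitting, fitting to Visit 7, and Visit 7 to Visit 9. Use each subject's actual fitting date as the boundary, since Protocol 6.18 allows fitting to be delayed. Take subjects still in follow-up at the start of each period as the denominator and print that number. Keep the cumulative column. If cells are sparse, give the periods only for the totals and predefined categories, and leave SOC and PT detail cumulative.

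For the 6-month analysis, add one sentence stating that adverse events are counted up to each subject's own Visit 7.

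The cost is SAP wording, some programming and a few extra columns with small counts. No new visit or assessment is needed. This assumes that the CRF records an onset date for each event. If it does not, the visit at which the event was recorded can assign the period, less precisely.
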